#### DLT-Equivalent Toxicity

A DLT-equivalent toxicity is defined as DLT event occurring in Cycle 3 or later.

Adverse event-related variables are listed below:

- **Adverse event (AE)** is defined as any untoward medical occurrence in a patient administered a pharmaceutical product, without regard to the possibility of a causal relationship.
- **AEs of special interest (AESIs)**

AESI for olaratumab:

- Infusion-related reactions (IRRs)

Notes: Categories of AESI may be modified as the understanding of the safety of the investigational drug increases. The final list of categories will be maintained at both compound and study level and reported in the clinical study report (CSR).

- Infusion Related Reactions (IRR) and delayed hypersensitivity reactions analysis uses the current standard Medical Dictionary for Regulatory Activities (MedDRA) Standardised Medical Queries (SMQs) to search for relevant events. Treatment-emergent adverse events are characterized as follows:
  - Anaphylactic reaction SMQ (narrow or algorithm per MedDRA SMQ guide )
  - Hypersensitivity SMQ (narrow) excluding PTs specific to injection site reactions
  - Angioedema SMQ (narrow)
  - Event maps to Preferred Term (PT) of Infusion related reaction
  - Event maps to PT of Cytokine release syndrome.

Medical review of each case identified by the algorithm above will be conducted prior to unblinding. Considerations for narratives and final designations include family history, pre-existing conditions, concomitant meds (e.g., was epinephrine used to treat), ruling out other confounding causes such as bee stings and food allergies, timing of the event, mechanism or biologic plausibility, and number of administrations. Such cases that clearly have a cause other than study drug will be excluded from the analyses.

Time frame: a day of infusion will be considered for immediate IRRs (i.e. immediate hypersensitivity reactions ). The 6 days after an infusion will be considered for delayed hypersensitivity reactions (i.e. if olaratumab is administered on Day 1 events occurred on Days 2 to 7 are considered; if olaratumab is administered on Day 8 events occurred on Days 9 to14 are considered).

- **Consolidated AEs** are composite AE terms consisting of synonymous Medical Dictionary for Regulatory Activities (MedDRA) preferred terms (PTs) to allow meaningful interpretation of the AE data. Consolidated AE categories and PTs will be maintained at compound level and reported in the CSR.
- **Serious adverse event (SAE)** is any AE that results in one of the following outcomes:
  - death
  - a life-threatening experience (that is, immediate risk of dying)
  - persistent or significant disability/incapacity
  - initial or prolonged in-patient hospitalization
  - congenital anomaly/birth defect
  - considered significant by the investigator for any other reason
- **Treatment-emergent adverse event (TEAE)** is defined as an event that first occurred or worsened in severity after baseline and 30 days after the last dose of study treatment and

related SAEs reported beyond 30 days after the last dose of study treatment, where last dose stands for actual dose, that is, 0 dose is not counted as last dose.

Exposure-related variables are listed below:

- **Dose exposures:** As reported in the eCRF
- **Number of dose level reductions:** Sum of the number of dose level reductions as reported in the eCRF
- **Dose delays:** As reported in the eCRF
- **Dose withheld/skip (Not Administered):** As reported in the eCRF
- **Dose interruption:** As reported in the eCRF

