7.2.2. Dosing Schedule

If any study drug is discontinued (olaratumab or chemotherapy), the patient will be discontinued from the trial. A change of body weight $\geq 10\%$ (increase or decrease) from baseline will result in re-calculation of dose to be administered.

The following treatments will be administered in this study every 3-week (21-day) ± 3 day cycle ([Table JGDN.7.1](#) and [Table JGDN.7.2](#)).

Part A:

Cycle 1

Olaratumab as IV infusion on Day 1 and Day 8 (at 15 mg/kg)

Cycle 2 and beyond

Olaratumab as IV infusion on Day 1 and Day 8 (at 15mg/kg, or 10 mg/kg if de-escalated),

AND

Doxorubicin as IV infusion on Day 1 and Day 2 (at 37.5 mg/m²; up to 6 cycles or a cumulative dose of 450 mg/m²)

OR

Vincristine as IV on Day 1 and Day 8 (patients ≥ 10 kg: 1.5 mg/m², patients <10 kg: 0.05 mg/kg. Dose is capped at 2 mg) plus irinotecan as IV on Days 1, 2, 3, 4, 5 (at 50 mg/m²),

OR

Ifosfamide as IV on Days 1, 2, 3, 4, and 5 (at 2.8 g/m²; up to 6 cycles or a cumulative dose of 84 g/m²). Treatment beyond 84 g/m² requires consultation with the Lilly CRP/CRS.

Part B:

Cycle 1

Olaratumab as IV infusion on Day 1 and Day 8 (at 20 mg/kg)

Cycle 2 and beyond

Olaratumab as IV infusion on Day 1 and Day 8 (at 20 mg/kg),

AND

Doxorubicin as IV infusion on Day 1 and Day 2 (at 37.5 mg/m²; up to 6 cycles or a cumulative dose of 450 mg/m²)

OR

Vincristine as IV on Day 1 and Day 8 (patients ≥ 10 kg: 1.5 mg/m², patients <10 kg: 0.05 mg/kg. Dose is capped at 2 mg) plus irinotecan as IV on Days 1, 2, 3, 4, 5 (at 50 mg/m²),

OR

Ifosfamide as IV on Days 1, 2, 3, 4, and 5 (at 2.8 g/m²; up to 6 cycles or a cumulative dose of 84 g/m²). Treatment beyond 84 g/m² requires consultation with the Lilly CRP/CRS.

Part C:

All Cycles

Olaratumab as IV infusion on Day 1 and Day 8 (at 20 mg/kg),

AND

Doxorubicin as IV infusion on Day 1 and Day 2 (at 37.5 mg/m²; up to 6 cycles or a cumulative dose of 450 mg/m²)

OR

Vincristine as IV on Day 1 and Day 8 (patients \geq 10 kg: 1.5 mg/m², patients <10 kg: 0.05 mg/kg. Dose is capped at 2 mg) plus irinotecan as IV on Days 1, 2, 3, 4, and 5 (at 50 mg/m²),

OR

Ifosfamide as IV on Days 1, 2, 3, 4, and 5 (at 2.8 g/m²; up to 6 cycles or a cumulative dose of 84 g/m²). Treatment beyond 84 g/m² requires consultation with the Lilly CRP/CRS.

Table JGDN.7.1. Treatment Regimens/Dosing Schedule (Parts A and B)

Study Drug		Dose	Route	Timing

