- summary of consolidated treatment-emergent SAEs
- summary of study drug-related consolidated treatment-emergent SAEs

A listing of SAEs will be produced.

The following death reports will be provided:

- summary of deaths (all deaths and deaths within 30 days of last dose of study drug)

The following AE of special interest (AESIs) summary will be provided:

- summary of treatment-emergent AESIs by AESI group and PT (regardless of causality and study drug-related)
- listing of treatment-emergent AESIs

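### The olaratumab infusion-reaction analysis can retain reactions to chemotherapy infused alone on Days 2 to 5, because its exclusion rule covers only causes other than study drug

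*SAP*

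**What the plan says.** The AESI text in SAP 5.3.1 sits below the DLT-Equivalent Toxicity heading. It names one AESI for olaratumab, infusion-related reactions, and then gives a joint rule for infusion-related and delayed hypersensitivity reactions.

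- **Search.** Treatment-emergent events are selected by standardised MedDRA queries (anaphylactic reaction, hypersensitivity, angioedema) and two preferred terms (infusion related reaction, cytokine release syndrome).
- **Timing.** An event on a day of infusion is immediate; no drug is named. For later events: "The 6 days after an infusion will be considered for delayed hypersensitivity reactions". The SAP's examples tie this window to olaratumab: "if olaratumab is administered on Day 1 events occurred on Days 2 to 7 are considered" and "if olaratumab is administered on Day 8 events occurred on Days 9 to14 are considered".
- **Review.** Every case found is reviewed medically, with attention to confounding causes, timing and mechanism. Then: "Such cases that clearly have a cause other than study drug will be excluded from the analyses".
- **Output.** SAP 5.9.2 plans a "summary of treatment-emergent AESIs by AESI group and PT", once regardless of causality and once for study drug-related events, plus a listing.

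Protocol 7.2.2 gives olaratumab on Days 1 and 8. The chemotherapy days differ by regimen. For example: "Ifosfamide as IV on Days 1, 2, 3, 4, and 5". Irinotecan is also given on Days 1 to 5, doxorubicin on Days 1 and 2, and vincristine on Days 1 and 8.

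**The concern.** The search finds a type of event and the window gives it a date. Neither identifies the drug. In a combination cycle, the days after the Day 1 olaratumab dose are also days on which another intravenous drug is running, so an acute reaction to that drug can fall in the delayed olaratumab window.

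The medical review is the only safeguard, and its exclusion sentence names the wrong reference. It should separate olaratumab from everything else. It separates study drug from everything else, and study drug includes the chemotherapy.

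Protocol 5.3 calls infusion-related reactions an important identified risk of olaratumab, and they are the only AESI named in the SAP. If chemotherapy reactions remain in the count, its delayed part will depend partly on how many chemotherapy-only infusion days a regimen has. Part C patients have no olaratumab monotherapy cycle at entry to serve as a reference.

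**Working it through.** **1. Reproduce the SAP's window.** Olaratumab days are 1 and 8 (Protocol 7.2.2). Adding 1 to 6 days gives Days 2 to 7 and Days 9 to 14, as the SAP states. That is 6 + 6 = 12 window days per 21-day cycle.

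**2. Intersect the window with the chemotherapy days in Protocol 7.2.2.**

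| Treatment | Infusion days | Shared with olaratumab | Chemotherapy-only days in window | Share of 12 |
|---|---|---|---|---|
| Doxorubicin | 1, 2 | 1 | Day 2 | 1 of 12 |
| Irinotecan | 1 to 5 | 1 | Days 2 to 5 | 4 of 12 |
| Vincristine | 1, 8 | 1, 8 | none | 0 of 12 |
| Ifosfamide | 1 to 5 | 1 | Days 2 to 5 | 4 of 12 |
| Olaratumab alone (Parts A and B, Cycle 1) | none | none | none | 0 of 12 |

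All the overlap lies in the window after the Day 1 dose: 4 of its 6 days for irinotecan and ifosfamide, 1 of 6 for doxorubicin. The Day 9 to 14 window has none. The opportunity per combination cycle is therefore 4 to 1 between the two five-day regimens and doxorubicin, and nil in monotherapy.

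**3. What study drug means.**

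- Protocol 7.2.2: "If any study drug is discontinued (olaratumab or chemotherapy), the patient will be discontinued from the trial".
- Protocol Tables JGDN.7.1 and JGDN.7.2 list all four chemotherapy agents in the study drug column.
- SAP 5.9.2 treats a missing relationship as related to all study drugs, in the plural, and its listing of discontinuations groups olaratumab and chemotherapy with any study drug.

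**4. Trace one event.** Take a preferred term of infusion related reaction with onset during a Day 3 ifosfamide infusion.

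- The search selects it.
- Day 3 lies in Days 2 to 7, so it falls in the delayed window.
- Review may conclude that ifosfamide is the clear cause. Ifosfamide is a study drug, so the stated exclusion does not apply.
- The event qualifies for the version regardless of causality and for the study drug-related version. Neither is specific to olaratumab.

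**5. What cannot be computed.** Turning infusion days into patients needs a reaction rate per infusion for each agent, the number of combination cycles received, and the proportion of cases reclassified at review. The documents give none of these, so no event count is offered.

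**The case against.** The strongest reply is that the search only opens the case. Final designation follows a review that must weigh confounders, timing and plausibility, and a reaction during a chemotherapy infusion is what such a review would notice. *Study drug* also appears beneath a line about olaratumab, and reviewers may read it that way. A broad search followed by clinical review is a defensible safety choice. Sites attribute reactions too: Protocol 7.2.4.1.1 asks for antibody and PK samples after a reaction to olaratumab. With at most 79 patients, the listings can be read against dosing dates.

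Much of this stands, and it limits the point. A reader might infer that:

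- **Chemotherapy reactions are automatically counted as olaratumab events.** The documents do not support that. Such events can be retained because no rule requires their removal; reviewers may still reclassify them.
- **Rates in the five-day arms will be inflated by a known amount, or will exceed those with doxorubicin.** Only the opportunity is known to be unequal. Without agent-specific rates, neither the size nor the direction of a difference in events follows.
- **Delayed events certainly enter the AESI table.** The rule is written within the AESI definition and no other output for them is specified, but the SAP does not say so outright.
- **Dose decisions are affected.** They are not driven by this window. DLTs have their own definition, the analyses are descriptive (SAP 5.2), and no between-arm AESI comparison is planned.

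The reply does not rescue the exclusion sentence. Reviewers who follow it literally would keep a case they believe chemotherapy caused.

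**Conclusion.** The point holds as a wording and attribution gap. An analysis labelled for olaratumab has a time window containing 4 chemotherapy-only infusion days per cycle with irinotecan or ifosfamide, 1 with doxorubicin and 0 in the monotherapy cycle. Its stated exclusion does not remove a reaction clearly caused by the chemotherapy.

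The day counts follow from the nominal schedule alone. The conclusion about the exclusion rests on giving *study drug* the meaning it has elsewhere in both documents. The effect on reported rates is unknown and may be small. Severity is minor; the case for change is that it is cheap and affects the reporting of an important identified risk.

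**What to change.** In SAP 5.3.1:

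1. In the exclusion sentence, replace *study drug* with *olaratumab*.
2. State that *infusion* in the time-frame rule, for immediate and delayed reactions alike, means the olaratumab infusion.
3. Flag each identified event whose onset date is a day with chemotherapy but no olaratumab. Use actual dosing dates, because Attachment 1 allows visits to move by up to 3 days.
4. Report the infusion-related and delayed hypersensitivity summary with and without the flagged events, by combination arm, with the Part A and B monotherapy cycle shown separately.

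The cost is two wording changes and one derived flag from onset and dosing dates already collected. There is no new data collection and no change to treatment. The downside is that a true delayed olaratumab reaction on a chemotherapy-only day will be flagged, but it stays visible because both versions are shown. The flag does not help on shared infusion days (Day 1, and Day 8 with vincristine). There, attribution still depends on medical review, now with olaratumab as the stated reference.

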8.1.2.2.3. Follow-Up Visit

All AEs and SAEs, regardless of relatedness to study drug(s) or protocol procedures, occurring during the follow-up visit (Visit 801) must be reported to Lilly or its designee. The follow-up visit (Visit 801) starts one day after the decision is made to discontinue the patient from the study. At the end of the follow-up visit, the patient will be required to have specific safety assessments ([Attachment 1](#)). The timing of these safety assessments is 30 days \pm 7 days after the decision is made to discontinue the patient from the study.

Following the safety assessments, which mark the end of the follow-up visit (Visit 801), the patient will be discontinued from the study, unless there is an ongoing AE or SAE that is possibly related to study drug. In this instance, the patient should be followed in subsequent long-term follow-up visits until the event is resolved, the event is no longer considered to be drug-related, the event becomes stable or returns to baseline, a new treatment is initiated for the patient, or the patient dies or is lost to follow-up.

If it is deemed to be in the best interest of the patient to start a new anticancer treatment prior to the scheduled end of the follow-up visit, the follow-up visit duration may be shortened. In this case, the follow-up assessments should be completed prior to the initiation of the new therapy.

After the follow-up visit (Visit 801), AEs are not required to be reported unless the investigator feels the AEs were related to either study drug, drug delivery system, or a protocol procedure. If an investigator becomes aware of an SAE believed to be related to protocol procedures or study drug, the investigator should report the SAE to the sponsor, and the SAE will be entered in the Lilly Safety System.

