8.1.2.4. Summary of AE/SAE Reporting Guidelines

The AE and SAE reporting guidelines for enrolled patients are summarized in [Table JGDN.8.1](#).

Table JGDN.8.1. Adverse Event and Serious Adverse Reporting Guidelines for Patients Enrolled in Study JGDN

Timing	Types of AEs/SAEs Reported	Collection Database	Lilly Safety System
Prestudy (baseline assessments) (Starts at the signing of informed consent and ends just before the first dose of study drug)	Preexisting conditions All AEs All SAEs regardless of relatedness	x x x	x
On therapy (Starts at first dose of study drug(s) and ends at last dose of study drug(s))	All AEs All SAEs regardless of relatedness	x x	x
Follow-up Visit (Visit 801) (Starts one day after the decision is made to discontinue patient from study and ends when end of study safety assessments are completed [approximately 30 days later])	All AEs All SAEs regardless of relatedness	x x	x
Subsequent Follow-up visits, if necessary for patient monitoring	Ongoing AEs possibly related to study drug(s), or protocol procedures All SAEs related to protocol procedures or study drug	x x	x
Patient no longer on study	All SAEs related to protocol procedures or study drug that the investigator becomes aware of		x

Abbreviations: AEs = adverse events; SAEs = serious adverse events.

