## 5.6. Concomitant Medications

The following concomitant medications used during study treatment period or up to the 30-day postdiscontinuation follow-up period will be summarized by numbers and percentages by dose cohort, presented in decreasing frequency of the World Health Organisation drug term:

- all concomitant medications
- premedication for study drug

Patient listing of all concomitant therapies and premedications will be provided.

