### **5.9.3. Clinical Laboratory Evaluation**

The severity of laboratory results will be classified according to CTCAE Version 4.0. The shifts in CTCAE toxicity grading from baseline to worst postbaseline (first dose up to 30 days after the last dose of study treatment) grade will be produced.

A patient listing of all laboratory data will be provided with a flag for values outside of the laboratory normal range.

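### The TEAE and laboratory shift windows close 30 days after the last dose, so Visit 801 laboratory samples and late-onset AEs, timed from the decision to stop, can fall outside those summaries

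*SAP*

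**What the plan says.** Two SAP windows are tied to the last dose.

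- SAP 5.3.1 counts as treatment-emergent "an event that first occurred or worsened in severity after baseline and 30 days after the last dose of study treatment", and adds "related SAEs reported beyond 30 days after the last dose of study treatment". Last dose means the last dose actually given. The sentence has no word marking day 30 as an end point, but the related-SAE clause and the laboratory section make that the only sensible reading.
- SAP 5.9.3 produces shifts from baseline to "worst postbaseline (first dose up to 30 days after the last dose of study treatment) grade".

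The protocol ties the end-of-treatment safety visit to the decision to stop.

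- Protocol 8.1.2.2.3: "The follow-up visit (Visit 801) starts one day after the decision is made to discontinue the patient from the study". On the assessments themselves: "The timing of these safety assessments is 30 days", with a tolerance of ± 7 days, counted from that decision. All AEs and SAEs in the period are reported, related or not. The period may be shortened if new anticancer treatment is to start, with the assessments done first.
- Table JGDN.8.1 describes the same period: "Starts one day after the decision is made to discontinue patient from study and ends when end of study safety assessments are completed".
- The follow-up schedule in Attachment 1 requires hematology, coagulation, chemistry and urinalysis at this visit.

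SAP 5.6 summarizes concomitant medication "used during study treatment period or up to the 30-day postdiscontinuation follow-up period", so the SAP does use the discontinuation anchor for another data type.

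**The concern.** The protocol obliges sites to take a laboratory sample and collect AEs up to a date set by the decision to stop. The summary tables cut off at a date set by the last dose. When the two dates are some way apart, data that the protocol requires are gathered and then left out of the TEAE and laboratory shift summaries.

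Laboratory data are the more exposed. In every treatment schedule in Attachment 1, chemistry is scheduled only on Day 1 of a cycle. A child who stops before the next Day 1 may therefore have Visit 801 as the only scheduled chemistry after the final cycle's doses; if the stop is in the first cycle, it is the only scheduled post-dose chemistry of all. Protocol 7.2.4.5.2 itself warns that ifosfamide-related renal impairment can go on worsening after the drug is stopped. A worst-grade table without the late sample can miss such a change.

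**Working it through.** The plan states no figure to reproduce; this is date arithmetic.

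**Inputs**

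- Window limit: day 30 after the last actual dose (SAP 5.3.1, 5.9.3).
- Visit 801 assessments: decision + 23 to decision + 37 days (Protocol 8.1.2.2.3).
- Last scheduled dose in a cycle: Day 8, olaratumab (Protocol 7.2.2). With a 21-day cycle, Day 8 to the next Day 1 is 14 days.
- Permitted treatment delay: up to 14 days (Protocol 7.2.4), so the gap can reach 14 + 14 = 28 days.
- g, days from last dose to decision: not stated. Assumed range 0 to 28, using the nominal schedule.

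**Laboratory sample.** An unshortened visit falls on day g+23 at the earliest and g+37 at the latest. The earliest visit is inside the window only if g + 23 ≤ 30, that is g ≤ 7.

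| g | Visit 801, days after last dose | Allowed visit days inside window |
|---|---|---|
| 0 | 23–37 | 8 of 15 |
| 7 | 30–44 | 1 of 15 |
| 8 | 31–45 | 0 of 15 |
| 14 (decision on next Day 1) | 37–51 | 0 of 15 |
| 28 (after a 14-day delay) | 51–65 | 0 of 15 |

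**AEs.** These are classed by onset or worsening, not by visit date, so the relevant quantity is the share of the follow-up period that lies inside the window. For a follow-up period of L days the share is min(L, 30 − g) / L. With L = 30:

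| g | Days inside | Share |
|---|---|---|
| 0 | 30/30 | 100% |
| 7 | 23/30 | 77% |
| 14 | 16/30 | 53% |
| 15 | 15/30 | 50% |
| 21 | 9/30 | 30% |
| 28 | 2/30 | 7% |

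At g = 14 the share is 16/23 = 70% for a visit at the early limit and 16/37 = 43% at the late limit. With a nominal visit, more than half of the follow-up days are lost only when g exceeds 15.

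**What is not cut.** Vital signs, ECG and ECHO/MUGA are summarized by time point with no 30-day limit (SAP 5.9.4). All AEs and all laboratory values are listed (5.9.2, 5.9.3). All deaths are summarized (5.9.2). Related SAEs count as TEAEs after day 30. The registry SAE summary ignores treatment emergence (5.15), although its table of other AEs is limited to non-serious TEAEs and so inherits the window.

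**The case against.** A reader might infer that most Visit 801 safety data are lost from the tables. The documents do not support that: the preceding list shows how much is summarized without a cut-off, and at a 14-day gap about half of the AE follow-up days still count.

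A reader might also infer that late toxicity is understated, chiefly in children who stop after a toxicity delay. That goes too far. Toxicity that causes a delay is present by about day 14, and a full delay ends about day 28, so that toxicity and any tests drawn during the delay lie inside the window. The shift table takes the worst grade, so a later recovery sample would not alter it. Clinically significant laboratory findings are reported as AEs as well (Protocol 8.1.2). Hematology is also drawn on Day 8, and on Day 15 of the first two combination cycles, so it depends less on Visit 801 than chemistry does. What survives is that new or worsening late abnormalities can be missed, not that they are.

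Three further points stand. The gap is nowhere stated, and some stops have none: a Grade 3 or 4 infusion reaction requires immediate discontinuation of olaratumab (Protocol 7.2.4.1.1). The visit may be brought forward for new therapy; a decision on day 14 with assessments 10 days later gives day 14 + 10 = 24, inside the window. And the concomitant-medication period in SAP 5.6 does not make the SAP contradict itself, since a medication window may properly differ from a TEAE window.

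Finally, the analyses are descriptive and the primary endpoint, DLT and exposure matching, is untouched. That limits the weight of the point. It does not restore the late chemistry or the late non-serious and unrelated events to the summaries.

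**Conclusion.** The mismatch of anchors is real and worth correcting, within limits. For an unshortened visit, the Visit 801 laboratory sample is always outside the shift table when the decision comes 8 or more days after the last dose. That includes a decision on the next scheduled Day 1 after a Day 8 dose. Because chemistry is scheduled only on Day 1, this can remove a patient's only scheduled post-dose chemistry. In a child who reaches the next Day 1, tests drawn to check readiness for dosing would soften the loss.

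Non-serious AEs and unrelated SAEs that start or worsen after day 30 fall outside the TEAE summaries; the follow-up time affected runs from none at g = 0 to 93% (28 of 30 days) at g = 28 for a nominal visit. How often each case arises cannot be determined, because the result rests on an assumed range for g. The effect is confined to the laboratory shift table and the summaries built on the TEAE definition.

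**What to change.** In SAP 5.3.1 and 5.9.3, run both windows from first dose to the later of 30 days after the last dose and the Visit 801 assessments, cut at the start of new anticancer therapy, with related SAEs counted thereafter as now. The cut agrees with Protocol 8.1.2.2.3, which already places the assessments before new therapy. The TEAE sentence should mark its end point explicitly at the same time. For a nominal visit the window would then close on day 37 at g = 7, day 44 at g = 14 and day 58 at g = 28; it stays at day 30 for g = 0.

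Alternatively, keep the 30-day window, state that the last-dose anchor is deliberate, and add one table of Visit 801 laboratory grades and AEs with onset or worsening after day 30.

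The first option costs two SAP sentences, slightly higher reported rates, and an observation window that varies by patient (up to 65 days after the last dose at g = 28) with some later unrelated events included. The second keeps a fixed window and costs one extra table. Neither needs new data.
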